### 4.5 SUBJECT POPULATIONS

All safety analyses will be conducted on all subjects who undergo treatment in any group.

The primary analysis on the primary endpoint will be performed on the ITT populations using the Multiple Imputation Methodology. The Multiple Imputation Methodology will use a mixed effects repeated measures model to predict the missing values. All Primary and Secondary endpoints will be analyzed using the ITT population.

It has been determined that any missing data in this study will follow the Missing at Random (MAR) assumption and is justified by the following section from the guide on missing data.

Missing Data Because of Attrition in the Course of the Study The longer the planned length of a clinical trial, the greater the chance that participants will drop out of the trial due to their moving out of the area or otherwise experiencing changes in their lives that preclude or complicate further participation. If dropping out due to these situations is known to be unrelated to changes in health status, an MAR assumption for the missing values seems justified;

Since none of these patients are likely to be in a life threatening disease situation and many have had knee pain for a period of time, the missing data will unlikely be due to any treatment effect or lack thereof. Previous studies have demonstrated a missing data rate of less than 1%. Thus, any missing data in this study follows that paradigm and thus should be considered MAR. Under this MAR assumption, the mixed effects repeated measures analysis yields unbiased estimates of the treatment effects and thus will be utilized in the analysis.

A secondary analysis will be conducted on the Per Protocol (PP) population. Since the primary endpoint is at 26 weeks, this is all subjects who complete the 26 week visit and who are not major violators of the protocol. For all other visits, this is defined as the subjects who complete those visits according to the protocol.

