9.9.7 Early Termination due to lack of efficacy in the Index knee

If a subject wants to obtain additional treatments such as HA and steroid injection in Index knee, the subject should undergo below assessment before receiving the additional treatment:

- Concomitant Medications
- Assess Adverse Events

- Confirm Rescue Medication Washout
- Count Rescue Medication Pills
- Evaluate Subject Electronic Diary
- Physical Evaluation (Both Knees)
- ROM (Both Knees) to be performed by Blinded Evaluator
- Evaluator Global Assessment to be performed by Blinded Evaluator
- WOMAC (Both Knees)
- VAS Pain Scale (Both Knees)
- NRS Pain Scale (Both Knees)
- EuroQoL-5D-5L
- Patient Global Assessment

After completing the assessment, the subject should be terminated from the study. These subjects will be considered as Treatment Failure.

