15.20 Subject Withdrawal

Each Subject is free to discontinue from the study at any time, for any reason. If a Subject discontinues the study, the Investigator will record the reason for withdrawal on the eCRF. Examples of reasons for premature withdrawal of a Subject from the study include:

- Inter-current illness that would, in the judgment of the Investigator, affect study assessment to a significant degree
- Subject noncompliance with follow-up assessments
- Subject request to withdraw
- Subject lost to follow-up
- Treatment failure
- Termination of the site's study participation by Anika Therapeutics, Inc., the institution, IRB or the Regulatory Authority
- Other (reason to be documented in the eCRF)

Every effort shall be made to have withdrawn subjects return for the required safety evaluations as detailed in the protocol.

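### SAP 4.5's case for missing at random does not cover the lack-of-efficacy terminations in protocol 9.9.7, leaves use of their exit WOMAC unstated, and plans no check on departures

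*SAP*

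**What the plan says.** **Rationale for MAR.** SAP 4.5 declares that any missing data will be MAR; protocol 11.8 says the same. The SAP supports this with an extract from a missing-data guide about people who move away or whose circumstances change. The extract attaches a condition, that such dropout is "known to be unrelated to changes in health status, an MAR assumption for the missing values seems justified". The SAP adds that "the missing data will unlikely be due to any treatment effect or lack thereof", and gives one figure: "Previous studies have demonstrated a missing data rate of less than 1" percent.

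**Imputation.** The only description is "The Multiple Imputation Methodology will use a mixed effects repeated measures model to predict the missing values". The anticipated code in SAP 4.1.2 is a single model restricted by `WHERE VISITNO = 26`.

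**Lack-of-efficacy exit.** Protocol 9.9.7 covers a subject who wants further index-knee treatment. It requires that "the subject should undergo below assessment before receiving the additional treatment", and the list includes the WOMAC. It then states: "After completing the assessment, the subject should be terminated from the study. These subjects will be considered as Treatment Failure". Protocol 15.20, under "Examples of reasons for premature withdrawal of a Subject from the study include", includes treatment failure.

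**Other analyses.** The week-26 per-protocol set is defined in SAP 4.5: "this is all subjects who complete the 26 week visit and who are not major violators of the protocol". SAP 4.6 adds only covariate models. The count of treatment failures runs through week 12 in SAP 4.1.4, but through week 26 in protocol sections 2 and 11.4.

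**The concern.** The guide extract and the SAP's own sentence both describe dropout that has nothing to do with how the knee is doing. The protocol creates a route out of the trial whose stated reason is that the knee is not doing well. For those subjects the argument offered for MAR does not apply, and no other argument is given.

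Whether MAR is tenable then depends on whether the recorded pain scores explain the exit. The most informative one is the WOMAC taken at termination. It is an unscheduled value and the week-26 model reads only week-26 rows, so it can matter only through the imputation, where no rule places it. If it is left out, and earlier visits do not fully account for the decision to leave, week-26 pain in these subjects will be imputed too favourably.

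Protocol 11.1 says the trial is designed to estimate the Cingal-TH difference, so a shift in that estimate bears on its main product. Nothing planned would reveal one. The week-26 per-protocol analysis omits the same subjects. Analyses at earlier visits include them but do not speak to week 26. The treatment-failure count could show an imbalance between arms but not its effect on the estimate, and in the SAP it leaves out the last 14 of 26 weeks.

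**Working it through.** **1. The plan's own figure.** Inputs from protocol 11.1 and SAP 4.1.1: 99 subjects in each of the Cingal and TH arms, SD 20, difference 8; two-sided 5% from SAP 4.1.2 and 4.2.

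- SE = 20 × √(2/99) = 2.84 mm.
- Power at 8 points: 80.4% (normal) or 80.0% (t), against the stated 80%.
- Power at 10 points: 94.0% or 93.8%, against the stated over 90%.

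The figures reproduce, so 2.84 is a fair yardstick. The 95% half-width is 1.96 × 2.84 = 5.57, and an observed 8 mm gives 2.43 to 13.57.

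**2. Size at the documented missing rate.** 1% of 231 is 2.31 subjects, about 2. To first order:

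shift = (difference between arms in the proportion of unrecovered failures) × (imputation error per failure)

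The documents give no imputation error. The simulations run for this point, on assumed trajectories, gave about 5 to 10 mm per failure. With a 1-point gap the shift is 0.01 × 5 to 0.01 × 10 = 0.05 to 0.10 mm. If all 2.31 missing subjects fell in one active arm, it is 2.31/99 × 10 = 0.23 mm. Both are negligible beside 2.84.

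**3. Size at assumed higher rates.** These failure rates are not in the documents.

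- 5-point gap: 0.05 × 5 to 0.05 × 10 = 0.25 to 0.5 mm.
- 10-point gap: 0.10 × 5 to 0.10 × 10 = 0.5 to 1.0 mm.

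**4. Does using the exit score help?** One simulation used 400,000 subjects per arm, SD 20, correlation 0.68 between weeks 18 and 26, and a true difference of 8 mm. Subjects improved by less than 5 mm could leave at week 9, 15 or 22. Its mean trajectories and termination probabilities are also assumed, so it shows mechanism and order of size only. Estimates in mm:

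| Failures %, Cingal / TH | Exit score unused | At actual time | Moved to next visit |
|---|---|---|---|
| 0.9 / 1.1 | 8.00 | 8.00 | 7.99 |
| 5.7 / 11.0 | 7.71 | 8.01 | 8.06 |
| 5.8 / 14.6 | 7.50 | 8.05 | 8.16 |
| 10.6 / 10.6 | 8.10 | 8.02 | 7.91 |
| 10.6 / 6.1 | 8.34 | 7.97 | 7.77 |
| 14.5 / 4.8 | 8.70 | 7.93 | 7.59 |

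With the score unused, the estimate moves in favour of whichever arm has more failures, by 0.3 to 0.7 mm in the unequal cases shown. Using the score at its actual time brings it back to 7.9 to 8.1. When exits coincided with scheduled visits, using the score recovered 8.00 exactly (from 7.71 at 10.2/14.6, and from 8.74 at 14.0/4.2).

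**5. Scale.** With the SE held fixed, moving the lower limit of an observed 8 mm to zero requires excess Cingal failures × error = 2.43 mm. That is 2.43/0.10 = 24 mm per failure at a 10-point excess, 2.43/0.05 = 49 mm at 5 points, and 2.43/0.01 = 243 mm at 1 point, which a 100 mm scale does not allow.

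**The case against.** **The SAP only says unlikely, and cites under 1%.** Protocol 9.9.7 provides an exit without showing that many will take it, and inclusion criterion 5 in protocol 8.1.1 requires willingness to abstain from other intra-articular treatment. This stands as to size. It does not repair the rationale: however few these exits are, the quoted condition does not describe them. The SAP also names no source for the rate and does not say whether those studies had a comparable exit.

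**Leaving for lack of efficacy does not make data not-MAR.** This stands in full. If exit depends on recorded scores and those scores are in the model, MAR can hold. A repeated-measures model also draws on the subject's earlier poor scores, and the daily diary (protocol 9.2.20) records pain between visits. What is missing is a statement that the exit score, or the diary, is used. A reader might infer that the primary analysis is biased; the documents do not support that.

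**Treatment failure is not the same as missing.** Also correct. The definition covers any non-rescue medication or procedure for the index knee, and protocol 15.9 keeps subjects with deviations in follow-up. A failure rate is therefore not a week-26 missing rate.

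**This is a pilot without formal testing (protocol 11).** That lowers the stakes, although SAP 4.1.2 does set out tests. An estimation study still needs a defensible estimate.

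**Placing the score at its actual time rather than the next visit is a preference.** Largely so: in the cases above the two differ by at most 0.34 mm (7.93 against 7.59).

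**Conclusion.** The point holds as a gap in justification and specification. The stated rationale for MAR does not cover a dropout route that the protocol itself creates; the rule that would make MAR credible for those subjects is absent; no planned analysis examines departures; and the two documents disagree on how long treatment failures are counted. Confidence in these textual findings is high.

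The numerical consequence is modest. It is negligible at the only documented missing rate. Under assumed failure rates differing by about 5 to 10 points, with 5 to 10 mm imputation error per failure, the shift is roughly 0.3 to 1 mm of 8, about a tenth to a third of the standard error. At near-equal rates, or if observed scores in the model explain the exits, there is little or none.

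Two further inferences should be resisted. One is that Cingal's advantage will be overstated: the direction depends on which arm has more unrecovered failures, and neither document gives rates by arm. The other is a bias of several millimetres or a reversed conclusion: that needs errors per failure well above those simulated, and nothing in the documents supports them.

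**What to change.** 1. In SAP 4.5, replace the sentence saying that missingness is unlikely to reflect effect or its absence. State MAR as an assumption conditional on observed scores, including the early-termination WOMAC. Align protocol 11.8.
2. State that this WOMAC enters the imputation model, either at its actual time since injection or in a pre-specified visit window. The choice is the sponsor's, but it should be fixed before unblinding.
3. Add one delta-adjusted (tipping-point) analysis, labelled as sensitivity only. Worsen the imputed week-26 scores of lack-of-efficacy terminations from 0 mm upward, for example in 5 mm steps, separately by arm, and report the Cingal-TH difference with its 95% interval.
4. Reconcile the treatment-failure window in SAP 4.1.4 with the protocol's week 26. Tabulate missing data and failures by arm and reason through week 26.

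The cost is SAP wording and a few extra model runs on data already collected, with no added subjects or visits and no change to the termination procedure. Using actual times needs a time-structured covariance and is not exactly unbiased (7.9 to 8.1 mm in the simulation), because subjects who stay have no score at those between-visit times.

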#### 4.6 ADDITIONAL ANALYSES

All of the analyses are performed on the data with the specified covariates or other factors assumed in the model. If it is determined that certain factors may influence the outcomes of the endpoints, then additional analyses will be performed. For the continuous variables, the factors will be added to the ANOVA model and evaluated in a stepwise fashion for significance. For the discrete variables, the data will be analyzed via a GEE model with the factors added to the model.
